9.5.16.1. Average Daily Prednisone Equivalent

Prior to carrying out calculations, each steroid must be converted to its prednisone equivalent and then the daily dose calculated using the frequency factors provided in

[Appendix 4](#): Prednisone Equivalent Conversion. Days on which the subject has no steroid use will be considered as 0mg.

Baseline

At baseline, the average daily prednisone equivalent dose is the sum of all prednisone doses over 7 consecutive days up to, but not including Day 1, divided by 7.

This will be derived for both steroids used to treat SLE and steroids used to treat all indications (SLE and non-SLE) separately. The baseline average daily prednisone dose for all indications will not be reported but will be used to carry out a cross-check against the randomization strata, which were determined by sites based on steroids received for any indication.

Treatment completion average dose

The average daily prednisone dose is the sum of all prednisone doses over 7 consecutive days up to and including the date of treatment completion, divided by 7.

This will be derived for steroids received for SLE only.

9.5.16.2. Average Daily Prednisone Dose during Weeks 40 to 52

The average daily prednisone dose during Weeks 40 to 52 is the sum of all prednisone doses from the day following the Week 40 visit date up to but not including the Week 52 study completion date divided by the number of days between Week 40 visit date and study completion date (study completion date – Week 40 visit date).

For subjects who withdraw from the study prior to the Week 40 visit date, the average daily prednisone dose during Weeks 40 to 52 will be missing.

For subjects who withdraw from the study after the Week 40 visit date, the average daily dose will be calculated as the sum of all prednisone doses from the day after the Week 40 visit date up to and including the date of withdrawal or death, whichever is earlier divided by the number of days between Week 40 visit date and the date of withdrawal or death, whichever is earlier (date of withdrawal or death – Week 40 visit date + 1). If the Week 40 visit is missing for any subject who has not withdrawn or died prior to Week 40, the Week 40 visit date will be imputed as treatment start date + 40 * 7 for this derivation.

This will be derived for steroids received for SLE only.

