4.2 Exclusion Criteria

Subjects will be excluded from participating in the study if they meet any of the following exclusion criteria:

1. Have received any prior treatment with belimumab, either as a marketed product or as an investigational agent.
2. Have received treatment with B cell targeted therapy (eg, rituximab, other anti-CD20 agents, anti-CD22 [epratuzumab], anti-CD52 [alemtuzumab], BLYS-receptor fusion protein [BR3], TACI-Fc, anti-BAFF [LY2127399]) within 364 days of Day 0.
3. Have received any of the following within 90 days of Day 0:
 - Any biologic agent (eg, adalimumab, etanercept, infliximab, anakinra) other than B cell targeted therapy (see Exclusion Criterion 2).
 - Plasmapheresis.
4. Have received any of the following within 60 days of Day 0:
 - A non-biologic investigational agent.
5. Have received any of the following within 30 days of Day 0:
 - A live vaccine.
6. Have a history of malignant neoplasm within the last 5 years, except for adequately treated cancers of the skin (basal or squamous cell) or carcinoma in situ of the uterine cervix.
7. Have required management of acute or chronic infections, as follows:
 - Currently on any suppressive therapy for a chronic infection (such as tuberculosis, pneumocystis, cytomegalovirus, herpes simplex virus, herpes zoster and atypical mycobacteria).
 - Hospitalization for treatment of infection within 60 days of Day 0.
 - Use of parenteral (IV or IM) antibiotics (antibacterials, antivirals, anti-fungals, or anti-parasitic agents) within 60 days of Day 0.
8. Have severe lupus kidney disease (defined by proteinuria > 6 g/24 hour or equivalent using spot urine protein to creatinine ratio, or serum creatinine > 2.5 mg/dL), or have severe active nephritis requiring acute therapy, or have required hemodialysis or high-dose prednisone or equivalent (> 100 mg/day) within 90 days of Day 0.
9. Have severe active central nervous system (CNS) lupus (including seizures, psychosis, organic brain syndrome, cerebrovascular accident [CVA], cerebritis or CNS vasculitis) requiring therapeutic intervention.
10. Known HIV infection.
11. Current or history of hepatitis B or hepatitis C infection.

12. Only applicable to Lithuanian sites:

- Have hypogammaglobulinaemia (IgG <400 mg/dL) or a deficiency in immunoglobulin A (IgA <10 mg/dL).
- Have had renal, stem cell/marrow or other major organ transplant.

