9.5.16. Prednisone

All prednisone analyses and summaries will consider SLE-related steroids only but data will also be derived for all indications steroids (SLE and non-SLE) for reference where indicated below.

The following will apply to all derivations in this section unless otherwise stated:

- For steroid use analyses, all steroid dosages are converted to a prednisone equivalent in milligrams; therefore, analyses refer to average daily prednisone dose instead of average daily steroid dose. See [Appendix 4: Prednisone Equivalent Conversion](#) for instructions on converting steroids to prednisone equivalents.
- This appendix will be updated throughout the course of the study to include all corticosteroids taken by subjects and will be finalized prior to the first database release and unblinding.
- For all derivations of the average daily prednisone equivalent dose including baseline, days on which a subject does not have prednisone use recorded will be considered as 0 mg for the day.
- Steroids taken intravenously (IV), intramuscularly (IM), subcutaneously (SC), intradermally, and orally are considered in prednisone dose derivations only.
- All steroids taken on any given day, including overlaps, will be accounted for in calculations of average daily prednisone dose. To achieve this programmatically, each entry is converted to the prednisone equivalent daily dose (see [Appendix 4: Prednisone Equivalent Conversion](#)) and the sum of the prednisone equivalent doses on Day X gives the total prednisone equivalent daily dose on Day X. For example, if two steroids are given on the same day they will be converted to a prednisone equivalent daily dose and then added together to achieve a total for that day.

Steroids used to treat SLE are those with medication type corticosteroid for SLE (SDTM.CM.CMCAT = 'CORTICOSTEROID FOR SYSTEMIC LUPUS ERYTHEMATOSUS').

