12.1. Major Efficacy Analyses

12.1.1. Percent of Subjects with Prednisone Reduction by $\geq 25\%$ from baseline to ≤ 7.5 mg/day during Week 40 through Week 52

Primary Analysis

For this analysis, only steroids used to treat SLE will be included and only subjects with a baseline average daily prednisone dose >7.5 mg/day will be included. See Section 9.5.16.1 for derivation of baseline prednisone dose and Section 9.5.16.2 for derivation of average prednisone use between Week 40 to Week 52.

The percent of subjects whose average prednisone dose has been reduced by $\geq 25\%$ from baseline to ≤ 7.5 mg/day during Weeks 40 through 52 will be compared between belimumab and placebo using a logistic regression model. Independent variables in the model will include treatment group, baseline prednisone dose, and the following

randomization stratification factors per the eCRF: screening SELENA SLEDAI score (≤ 9 vs. ≥ 10), and region. A responder is defined as having a prednisone reduction by $\geq 25\%$ from baseline to ≤ 7.5 mg/day during Weeks 40 through 52.

Any subject who withdraws from the study or adds new immunomodulatory agents used to treat SLE (note that this will include switches) prior to the Week 52 visit will be considered having no steroid reduction.

A summary of the number and percentage of subjects who are responders by treatment group, the treatment difference versus placebo, the odds ratio and 95% CI versus placebo, and a p-value for the odds ratio will also be provided.

Sensitivity Analysis

- To examine the robustness of the results, a sensitivity analysis of the SLE-related steroid reduction will be performed without considering any information related to the use of new immunomodulatory agents (note that this will include switches).

Additional Summaries of Prednisone

- A summary of the number and percentage of subjects with average SLE-related daily prednisone dose ≤ 7.5 mg/day and > 7.5 mg/day at baseline (Day 1) and treatment completion date will be presented for treatment completers.
- The cumulative SLE-related prednisone dose will be derived as described in Section 9.5.16.3. A table of descriptive statistics will be presented including the mean, standard deviation, median, 25th and 75th percentiles, minimum and maximum.
- A listing of cumulative SLE-related prednisone dose will be displayed by treatment and subject.

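### One IV or IM steroid dose in the 7-day baseline window can make a subject on an unchanged dose of 7.5 mg/day or less a steroid-reduction responder

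*SAP*

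**What the plan says.** All references to the RAP are to the Week 52 RAP in the SAP document.

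- **Baseline (9.5.16.1):** "the average daily prednisone equivalent dose is the sum of all prednisone doses over 7 consecutive days up to, but not including Day 1". The total is then divided by 7.
- **Routes and same-day doses (9.5.16):** "Steroids taken intravenously (IV), intramuscularly (IM), subcutaneously (SC), intradermally, and orally are considered in prednisone dose derivations only". Also, "All steroids taken on any given day, including overlaps, will be accounted for in calculations of average daily prednisone dose". No rule separates a one-off dose from maintenance dosing, and the frequency table in Appendix 4 gives 'Once' a factor of 1.
- **Indication (9.5.16):** the endpoint uses SLE steroids only. "Steroids used to treat SLE are those with medication type corticosteroid for SLE".
- **Outcome (9.5.16.2):** the Weeks 40-52 average runs from the Week 40 visit to study completion, about 84 days.
- **Analysis (12.1.1):** "only subjects with a baseline average daily prednisone dose >7.5 mg/day will be included". A responder needs both a reduction of at least 25% from that baseline and a Weeks 40-52 average of 7.5 mg/day or less. Leaving the study, or adding or switching an SLE immunomodulator, before Week 52 makes the subject a non-responder. The same derived baseline dose is a covariate in the logistic model.
- **Eligibility:** Protocol 4.1 asks for no stable steroid dose before Day 0. Exclusion criterion 8 in Protocol 4.2 bars subjects who needed "high-dose prednisone or equivalent (> 100 mg/day) within 90 days of Day 0".

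**The concern.** The endpoint is meant to show steroid sparing in subjects who were taking more than 7.5 mg/day. The entry threshold and the response ceiling are the same number, so the 25% rule is what separates a real taper from a trivial one. That rule is measured from an average over only 7 days, in which a single injection can dominate.

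A subject whose daily dose never changes can then be selected because of one injection and credited with a reduction because the injection was not repeated in a much longer window. Such subjects add responders who did not taper, and their covariate value is inflated. The only planned sensitivity analysis of this endpoint concerns new immunomodulators and leaves the baseline derivation untouched.

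**Working it through.** The documents give no sample size, power or response rate for this endpoint, so there is no stated figure to reproduce. The check applies the RAP's own derivation.

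**Inputs.** d = unchanged daily SLE steroid dose (mg/day). P = one SLE dose, in mg prednisone equivalent, within the 7 days before Day 1. Windows are 7 days and 84 days (Week 40 is Day 280 and Week 52 is Day 364 in the study calendar). The methylprednisolone conversion factor is 1.25 (Appendix 4), so 40 mg IM given once is 40 × 1.25 × 1 = 50 mg.

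**Formulas.**
- Baseline = d + P/7; Weeks 40-52 average = d.
- Entry: d + P/7 > 7.5, so P > 7(7.5 − d).
- 25% rule: d ≤ 0.75(d + P/7), so P ≥ 7d/3.
- Criterion 8, read as a limit on the day's total: d + P ≤ 100, so P ≤ 100 − d.

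**Weight of one dose.** A 50 mg dose adds 50/7 = 7.14 mg/day at baseline and 50/84 = 0.60 mg/day in Weeks 40-52. The ratio is 84/7 = 12.

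**Examples.**

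| d | P at baseline | Later dose, Weeks 40-52 | Baseline | Weeks 40-52 | Reduction | In subgroup | Responder |
|---|---|---|---|---|---|---|---|
| 5 | 50 | none | 12.14 | 5.00 | 58.8% | yes | yes |
| 7.5 | 50 | none | 14.64 | 7.50 | 48.8% | yes | yes |
| 5 | 50 | 50 | 12.14 | 5.60 | 53.9% | yes | yes |
| 7.5 | 50 | 50 | 14.64 | 8.10 | 44.7% | yes | no |
| 0 | 50 | none | 7.14 | 0 | n/a | no | n/a |
| 5 | 10 | none | 6.43 | 5.00 | n/a | no | n/a |
| 7.5 | 10 | none | 8.93 | 7.50 | 16.0% | yes | no |

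**Range of P that produces the artefact.** The two thresholds meet where 7.5 − d = d/3, at d = 5.625. At or below that dose, entry by this route already guarantees a 25% reduction, so the 25% rule adds no protection. Above it, the 25% rule sets the limit.

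- d = 0: P above 52.5, up to 100 mg
- d = 2.5: P above 35, up to 97.5 mg
- d = 5: P above 17.5, up to 95 mg
- d = 7.5: P from 17.5 to 92.5 mg

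**Literal reading of 9.5.16.2.** The sum there covers 83 days and the divisor is 84. This lowers the 17.5 mg threshold at d = 7.5 to about 16.7 mg. In the fourth row it gives 8.0 instead of 8.1. No conclusion changes.

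**The case against.** **The endpoint concerns average dose, not maintenance dose.** Protocol 8.5.3 defines it that way, and a steroid injected for SLE is SLE steroid use. Someone who needed an injection before Day 1 and none in Weeks 40-52 did use less. This is fair, but the third row of the table shows its limit. A subject on 5 mg/day with one 50 mg injection in each 84-day stretch averages 5.60 mg/day over both, yet is scored as a 53.9% reducer because the baseline window is 7 days.

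**Several filters already narrow the problem.** Non-SLE steroids and Day 1 doses do not count, and criterion 8 removes the largest pulses. All of this stands. A single injection of 100 mg equivalent on top of 5 or 7.5 mg/day totals 105 or 107.5 mg and is excluded on criterion 8's plain reading. The 50 mg examples are within the limit.

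**A check exists.** Section 10.3 cross-tabulates the randomisation and eCRF steroid strata. Sites counted all indications (8.2), so a subject randomised at 7.5 mg/day or less but above it on SLE steroids alone would stand out. That can flag only pulses the site did not count, and it does not re-run the endpoint.

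**Stronger readings to avoid.** A reader might infer that any such subject is automatically a responder. The last four rows of the table show otherwise, and withdrawal or a new immunomodulator also blocks response. A reader might also infer that, if a fraction q of the subgroup is affected, the treatment difference shrinks by (1 − q). That needs response in these subjects to be certain and unaffected by treatment, but withdrawal, new immunomodulators and later doses can all depend on treatment. Nor does the factor carry over directly to an adjusted odds ratio.

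**Conclusion.** The point holds as a possibility that the plan does not test. With one dose in the ranges above, a subject on an unchanged 7.5 mg/day or less can enter the subgroup and be scored as a responder, with apparent reductions of 59% and 49% in the two main examples. This assumes that the subject completes the study, adds no new immunomodulator and averages 7.5 mg/day or less in Weeks 40-52.

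The effect on the treatment comparison cannot be sized, because the documents do not say how many subjects had such doses. The doses precede first dosing under blinded randomisation, so the misclassification should be about equal by arm. It would mainly raise both response rates and dilute the contrast. Nothing in the documents suggests that it favours belimumab. Because the inflated baseline is itself the covariate, adjustment corrects only in part. Efficacy is secondary in this safety study, so this is a minor point with an inexpensive check.

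**What to change.** Keep the 12.1.1 analysis as it is and add one sensitivity analysis. Leave IV and IM SLE steroid records with frequency 'Once' out of both the baseline and the Weeks 40-52 averages. Use the recalculated baseline for subgroup entry, the 25% reference and the covariate. Removing these doses from baseline alone would create the opposite inconsistency. Report by arm how many subjects change subgroup or responder status; this count supplies the missing frequency.

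The Years 2 to 5 RAP (section 1) records unblinding of the Week 52 data on 2-JAN-2019, so an analysis added now must be labelled post hoc.

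The cost is one extra run on concomitant-medication data already collected, with a slightly smaller subgroup in that run. It does not capture short oral bursts or multi-day courses recorded as daily dosing.

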6.3 Treatment Period

Subjects will be evaluated at the study site for the scheduled study visits outlined in the Study Calendar (Table 6-1). On Day 0, the subject will be randomized and receive the first dose of study agent. Subjects will be dosed at Week 2, Week 4 and approximately every 28 days (calculated from the Day 0 dose) thereafter through Week 48. The final treatment period evaluation for the study will occur at Week 52. Time windows are defined as ± 3 days for visits at Week 2 and Week 4, and ± 7 days for visits from Week 8 through Week 52. All study visits should occur within the visit window of the scheduled study visit. In rare circumstances, when the scheduled visit cannot be done within the visit window the Medical Monitor may be contacted for advice. Similarly, while all assessments for a dosing visit should be performed same day, in rare circumstances, an investigator may be permitted to conduct the assessments over two consecutive days so long as the infusion of the study agent is performed on the second day and after all other assessments.

All subjects who do not withdraw consent to participate in the first year monthly study visits and regardless of whether they continue to receive study agent will be followed on-study through Week 52 and annually for Years 2 through 5 (Week 260). All subjects will have a follow-up visit performed approximately 4 weeks after the last dose of study agent. In the event that a subject withdraws consent to participate in the first year monthly study visits, an attempt should be made at the time of consent withdrawal to obtain consent to contact the subject at Week 52 and annually for Years 2 through 5 (Week 260) to assess mortality and malignancy (including NMSC).

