1. INTRODUCTION

The purpose of this reporting and analysis plan (RAP) is to describe the summaries to be included in the Clinical Study Report for the Years 2 to 5 post-treatment follow-up period for the HGS1006-C1113 study and the annual summaries for reporting to regulatory authorities. The study will be reported under its GSK study number BEL115467.

A separate RAP describes the safety and efficacy analyses that were performed through the Week 52 double-blind treatment period. A RAP Addendum prospectively describes additional safety analyses to supplement the planned analyses through the Week 52 double-blind treatment period specified in the main RAP. Summaries and analyses for the Week 52 double-blind treatment period have been produced and reported. The RAP for the Week 52 double-blind treatment period was finalized on 18-OCT-2018. The RAP Addendum was finalized on 13-DEC-2018. Data from the Week 52 double-blind treatment period was unblinded on 2-JAN-2019 and Statistical Analysis Complete (SAC) was achieved on 7-FEB-2019.

The Years 2 to 5 post-treatment follow-up period RAP was finalized on 23-SEP-2019, after unblinding and SAC for the Week 52 double-blind treatment period part of the study but prior to the Year 2 follow-up reporting. The Year 2 SAC, following this RAP, was achieved on 20-DEC-2019.

This amendment to the Years 2 to 5 post-treatment follow-up period RAP was created after the Year 2 follow-up reporting and finalised before the Year 3 follow-up reporting. It addresses: 1) adding commercial Benlysta use to listings for subjects who died or had malignancies, 2) removing the GSK (manually assigned) PSAP category death and malignancy outputs (for the reasons given in Section 5.6) and 3) adding 2 additional COVID-19 death summaries.

This is a global, multi-center, randomized, double-blind, placebo-controlled, 52-week study to assess mortality and adverse events of special interest (AESI) in adults with active, autoantibody-positive systemic lupus erythematosus (SLE) treated with belimumab plus standard therapy vs placebo plus standard therapy. Following the 52-week study, all subjects were to be contacted annually through Year 5 (Week 260) to assess mortality and malignancy (including non-melanoma skin cancers [NMSC]).

This RAP is based upon the following study documents:

- Study Protocol Amendment 03 (May 22, 2017)
- Final Case Report Form (CRF) Version 6.2 (June 19, 2017)

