2.3. Statistical Hypotheses

There are no formal statistical hypotheses for the primary safety endpoints in the study. The main purpose of this study is to provide an evaluation of the difference in the rates of all-cause mortality and all prespecified AESI between the belimumab and placebo groups with a 2-sided 95% CI. SAEs will be summarized descriptively only. See Section [11.1.2](#) for details of the protocol-defined AESIs.

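### For completers, the Week 40–52 average prednisone dose is divided by one day more than is summed (83 doses over 84 days at target visits), so it is about 1.2% too low as written (minor)

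*SAP*

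**What the plan says.** Section 9.5.16.2 of the Week 52 RAP defines the average for subjects who complete the study. The numerator reads: "sum of all prednisone doses from the day following the Week 40 visit date up to but not including the Week 52 study completion", so both end dates are left out. The total is then "divided by the number of days between Week 40 visit date and study completion date (study completion date – Week 40 visit date").

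Subjects who leave after Week 40 have their own rule. Doses are summed from the day after the Week 40 visit through the day of withdrawal or death, and the divisor is given as "date of withdrawal or death – Week 40 visit date + 1".

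The baseline average in section 9.5.16.1 is the "sum of all prednisone doses over 7 consecutive days up to, but not including Day 1, divided by 7".

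Section 12.1.1 applies the Week 40–52 average to the responder rule, which requires a reduction of at least 25% from baseline to 7.5 mg/day or less, among subjects above 7.5 mg/day at baseline. Under the same section, "Any subject who withdraws from the study or adds new immunomodulatory agents used to treat SLE" before the Week 52 visit counts as having no steroid reduction.

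**The concern.** An average needs as many days in its divisor as in its sum. Section 9.5.16 sets days without recorded steroid to 0 mg, so every day in the window carries a value and the divisor should simply be the window length. For completers the bracketed formula is one day longer than the window, so even a constant dose averages to less than itself.

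The responder rule then compares a correctly averaged baseline with an understated Week 40–52 value. This is the major efficacy endpoint, analysed by logistic regression with an odds ratio, confidence interval and p-value. A rule that does not apply its own stated thresholds should be corrected, even when the shift is small.

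**Working it through.** **Inputs.** The target study days are 281 for Week 40 and 365 for Week 52 (Week 52 RAP 9.5.3). Protocol 6.3 gives a visit window of plus or minus "7 days for visits from Week 8 through Week 52". The responder thresholds are those in 12.1.1. The plan states no numeric result to reproduce, only the rule. Write V for the Week 40 visit day and C for the completion day.

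**Day count for completers**
- Days summed: V + 1 to C − 1, which is C − V − 1 days.
- Divisor as written: C − V.
- Ratio of the written average to the true average over the summed days: (C − V − 1)/(C − V), an understatement of 1/(C − V).

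**Effective thresholds.** The 7.5 mg/day limit acts as 7.5 × (C − V)/(C − V − 1). The 25% reduction acts as 1 − 0.75 × (C − V)/(C − V − 1).

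| V, C | Summed / divisor | Understated by | 7.5 mg/day acts as | 25% acts as |
|---|---|---|---|---|
| 281, 365 (target) | 83 / 84 | 1.19% | 7.59 | 24.1% |
| 288, 358 (shortest in-window gap) | 69 / 70 | 1.43% | 7.61 | 23.9% |
| 274, 372 (longest in-window gap) | 97 / 98 | 1.02% | 7.58 | 24.2% |

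**Which cut-off binds.** The effective limit for a subject is the smaller of 7.5 and 0.75 × baseline. The two are equal at a baseline of 10 mg/day. Above that the 7.5 mg/day limit binds; between 7.5 and 10 mg/day the 25% reduction binds.

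**Who is reclassified, at target days.** A completer changes status when the Day 282–364 total lies above cut-off × 83 but not above cut-off × 84:
- Baseline 10 mg/day or more: above 7.5 × 83 = 622.5 mg and at most 7.5 × 84 = 630 mg.
- Baseline 8 mg/day (cut-off 6 mg/day): above 6 × 83 = 498 mg and at most 6 × 84 = 504 mg.

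The written divisor is always the larger one, so every change is from non-responder to responder. A subject on a constant 7.5 mg/day with a baseline of at least 10 mg/day passes either way.

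**Illustrative single step-downs** (assumed regimens, baseline 10 mg/day or more, k days at the higher dose then 83 − k at the lower, so 84 possible values of k):
- 10 to 5 mg/day: total 415 + 5k falls in the band for k = 42 and 43 (2 of 84).
- 15 to 5 mg/day: total 415 + 10k falls in the band for k = 21 (1 of 84).
- 8 to 7 mg/day: total 581 + k falls in the band for k = 42 to 49 (8 of 84).

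**Withdrawal or death branch.** Days summed are W − V, where W is the day of withdrawal or death, and the divisor is W − V + 1. For withdrawal on Day 300, Days 282–300 give 19 doses and the divisor is 300 − 281 + 1 = 20. The same one-day surplus appears, but it cannot alter response because 12.1.1 already makes study withdrawals non-responders.

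**The case against.** The strongest objection is that the text shows only that sum and divisor disagree, not which is wrong. Adding the completion day to the sum would give 84 doses over 84 days and leave the written divisor intact. The shortfall would then be that one day's dose divided by 84, and the illustrations would change. With the completion day at the lower dose, the corrected totals must satisfy 420 + 5k ≤ 630, 420 + 10k ≤ 630 and 588 + k ≤ 630. The number of positions that change status becomes one, none and seven, instead of two, one and eight. Starting the sum on the Week 40 visit date would also reconcile both branches (84/84, and 20/20 for Day 300). This stands as a condition on the illustrative counts. It does not remove the mismatch. The summed window is explicit, and a count of days between two dates also suggests 83, so the bracket is the outlier.

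A second objection is that the bracket may be loose shorthand and the program may have used the right count. The documents do not show what was programmed, so an error in the reported results is not established. The finding concerns the rule as written.

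Third, 1.0% to 1.4% is not a strict bound. The completion date comes from the study conclusion record (9.5.8), and Protocol 6.3 foresees rare out-of-window visits. That is correct.

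Finally, the practical effect is slight. The rule is the same in both arms, the efficacy endpoints are secondary, and section 2.3 states that "The main purpose of this study is to provide an evaluation of the difference in the rates of all-cause mortality and all prespecified AESI". All of this supports a minor rating.

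**Conclusion.** The rule is wrong as written, and the point is minor. For completers the Week 40–52 average is understated by 1.2% at target days, and by 1.0% to 1.4% across the in-window visit gaps. The responder thresholds become about 7.59 mg/day or 24.1%. These sizes assume that the summed window is the intended one and that the bracketed formula is followed literally.

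Only completers within about one day's dose above their binding cut-off are affected, and always in the direction of response. Completers who add or switch immunomodulatory agents are non-responders in the main analysis regardless. The number of subjects in the band is not in the documents, and no bias in the treatment comparison is claimed.

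**What to change.** In section 9.5.16.2 make each divisor equal the number of days summed:
- Completers: study completion date − Week 40 visit date − 1.
- Withdrawal or death, for consistency only: date of withdrawal or death − Week 40 visit date.

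If the sponsor intended a window that includes one of the end dates, it should say so and change the sum instead; either way the two counts must agree.

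A text edit alone is not enough, because section 1 of the Years 2 to 5 RAP records: "Data from the Week 52 double-blind treatment period was unblinded on 2-JAN-2019 and Statistical Analysis Complete (SAC) was achieved on 7-FEB-2019". The sponsor should also document which day count was programmed. If it was the literal one, rerun the 12.1.1 analysis and its sensitivity analysis with the matched divisor, label the rerun as a post-unblinding correction, and report by arm how many subjects change status.

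The cost is two formula edits and one documentation note, with no new data, plus one rerun of the steroid-reduction tables only if the literal formula was used.
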